8.6 Measures of Treatment Compliance

N/A

9 STUDY PROCEDURES AND GUIDELINES

A ‘Schedule of Events by Study Visit’ representing the required testing procedures to be performed for the duration of the study is diagrammed in [Appendix E](#). All subject visits will be documented in the Subject Tracking Log ([Appendix F](#)). See [16 Data Collection, Retention, and Monitoring](#), for details.

Prior to conducting any study-related activities, written informed consent and the Health Insurance Portability and Accountability Act (HIPAA) authorization must be signed and dated by the subject.

Subjects will be compensated for their time and travel expenditures, up to \$200 total. Subjects will be paid up to \$50 for completion of each study visit, and up to an additional \$50 upon completion of all study visits.

9.1 Clinical Assessments

All clinical assessment information will be collected on study-specific forms.

9.1.1 Concomitant Medications

All concomitant medication and concurrent therapies will be documented during the Phone Screen, and re-confirmed at lab visits.

9.1.2 Demographics

Demographic information (date of birth, gender, race) will be recorded during the Phone Screen and confirmed at visit 1.

9.1.3 Medical History

Relevant medical history, including history of or current disease and other pertinent medical history will be recorded at the Phone Screen.

9.1.4 Physical Examination

Height and weight will be measured at visit 1.

9.1.5 Vital Signs

Blood pressure will be measured at visit 1.

9.1.6 Adverse Events

Information regarding occurrence of adverse events will be captured throughout the study. Duration (start and stop dates), severity, outcome, treatment and relation to study drug will be recorded on case report forms (CRFs).

92 Clinical Laboratory Measurements

9.2.1 Pregnancy Test

A urine pregnancy test will be obtained from all subjects at visit 1.

9.2.2 Urinalysis

Urine will be obtained for pregnancy testing and testing for opioid drug/medication use at visit 1.

10 EVALUATIONS BY VISIT

Table 1. Study events, description, and length of time involved

Event	Description	Length
Web-based eligibility	Screening for self-report eligibility (inclusion and exclusion) criteria	<15 minutes

screening		
Phone Screen	Confirm eligibility criteria Schedule baseline assessment Review food buffet menu options	<15 minutes
Visit 1	Screening for specimen-based exclusion criteria Self-report measures of eating behavior Computerized cognitive tasks Test or control product administration day 1	1.5 to 2 hours
Visit 2	Test or control product administration day 2	1.5 to 2 hours

Web-based eligibility screening:

- Subjects who meet all inclusion criteria and who have none of the exclusion criteria on the UCSF-hosted web-based eligibility screening website (wherein they provide their phone number) will be called by study staff to complete the Phone Screen.

Phone Screen:

- Verify Eligibility: Review inclusion and exclusion criteria with subject to ensure eligibility, including relevant medications, demographics, and medical history.
- Review Protocol: Review study protocol to ensure subject's willingness to partake in each component of the study, including the time commitment and locations of visits 1 and 2, as well as self-report measures, a urine screen for pregnancy and opiate drug/medication use, eating pre-selected foods from a "buffet" of preferred foods at two study visits, receiving the intranasal naloxone and intranasal placebo, and providing saliva samples.
- Schedule Visits 1 and 2: Schedule subject's visits 1 and 2. There will be a period of at least 24 hours between visits 1 and 2, and, as the period of time between each administration day does not impact analyses assessing primary or secondary outcomes, the amount of time between administrations will vary according to the subject's schedules so as to reduce subject burden.

Visits 1 and 2: Control Product and Test Product Administration Visits:

- Location: Subjects will present to the UCSF Mount Zion Campus, [name].
- Clinical Assessments Conducted by Study Staff:
 - Objective Weight and Height Measures: Staff will collect the subject's height and weight.
 - Blood pressure: Staff will collect blood pressure.
 - Pregnancy and Opiate Drug/Medication Screen: Staff will collect a urine sample to test for pregnancy and use of opioid drugs/medications.
- Randomization: [name] will report the subject's ID number and eligibility status to the unblinded study staff, who will consult the randomization table generated by the UCSF Research Pharmacy staff (which will dictate the ordering in which the subject will receive the test and control products at each visit).
- Taste Test Procedure: At visits 1 and 2, subjects will eat for 10 minutes from a food buffet that includes foods that they selected during visit 1 (different foods will be provided at each visits 1 and 2 so as not to repeat foods). All foods will be served in

large bowls and in large quantities, factors that are known to non-consciously increase intake⁴⁰. Bowls of food will be weighed before and after the “taste test” period and this information will be documented ([Appendix H](#)). As commonly done in studies involving hedonic eating, subjects will indicate (on paper forms) how much they liked each food on paper questionnaires after tasting each food, as done in prior studies examining the role of opioid involvement in liking of foods^{41,42}.

- *Administration of Test Product (Intranasal Naloxone) or Control Product (Intranasal Placebo)*: Subjects will receive each the test product (intranasal naloxone) (2 mg/ 2 mL, 1 mg/1 mL per nostril) and control product (intranasal placebo, 1 mL per nostril) via a nasal mucosal atomization device (MAD; [See 8.4.3 Syringe Assembly](#)) in a randomized order (per the randomization table generated by the UCSF Research Pharmacy and accessible only to unblinded study staff) on visits 1 and 2, immediately following the food buffet procedure.
- *Self-Report Measures*: Subjects will self-report their level of nausea (present versus absent) in the context of completing the SOWS³ prior to receiving either the test or control product, as well as 10 and 30 minutes after receiving the test or control product.
- *Saliva Samples (Salivary Cortisol)*: Subjects will provide saliva samples prior to receiving the test and control products, as well as 20 and 50 minutes after receiving the test or control products.

11 ADVERSE EXPERIENCE REPORTING AND DOCUMENTATION

11.1 Adverse Events

An adverse event (AE) is any untoward medical occurrence in a clinical investigation of a subject administered a pharmaceutical product and that does not necessarily have a causal relationship with the treatment. An AE is therefore any unfavorable and unintended sign (including an abnormal laboratory finding), symptom or disease temporally associated with the administration of an investigational product, whether or not related to that investigational product. An unexpected AE is one of a type not identified in nature, severity, or frequency in the current Investigator’s Brochure or of greater severity or frequency than expected based on the information in the Investigator’s Brochure.

The Investigator will probe, via discussion with the subject, for the occurrence of AEs during each subject visit and record the information in the Adverse Event Accountability Log ([Appendix I](#)) and in the subject’s CRF. Adverse events will be described by duration (start and stop dates and times), severity, outcome, treatment and relation to study drug, or if unrelated, the cause.

AE Severity

The guidelines shown in Table below should be used to grade severity. It should be pointed out that the term “severe” is a measure of intensity and that a severe AE is not necessarily serious.

Table 3. AE Severity Grading

Severity (Toxicity Grade)	Description
Mild (1)	Transient or mild discomfort; no limitation in activity; no medical intervention or therapy required. The subject may be aware of the sign or symptom but tolerates it reasonably well.
Moderate (2)	Mild to moderate limitation in activity, no or minimal medical intervention/therapy required.
Severe (3)	Marked limitation in activity, medical intervention/therapy required, hospitalizations possible.
Life-threatening (4)	The subject is at risk of death due to the adverse experience as it occurred. This does not refer to an experience that hypothetically might have caused death if it were more severe.

AE Relationship to Study Drug

The relationship of an AE to the study agent should be assessed using the following the guidelines in Table .

Table 4. AE Relationship to Study Drug

Relationship to Drug	Comment
Definitely	Previously known toxicity of agent; or an event that follows a reasonable temporal sequence from administration of the drug; that follows a known or expected response pattern to the suspected drug; that is confirmed by stopping or reducing the dosage of the drug; and that is not explained by any other reasonable hypothesis.
Probably	An event that follows a reasonable temporal sequence from administration of the drug; that follows a known or expected response pattern to the suspected drug; that is confirmed by stopping or reducing the dosage of the drug; and that is unlikely to be explained by the known characteristics of the subject's clinical state or by other interventions.
Possibly	An event that follows a reasonable temporal sequence from administration of the drug; that follows a known or expected response pattern to that suspected drug; but that could readily have been produced by a number of other factors.
Unrelated	An event that can be determined with certainty to have no relationship to the study drug.

11.2 Serious Adverse Experiences (SAE)

An SAE is defined as any AE occurring at any dose that results in any of the following outcomes:

1. death
2. a life-threatening adverse experience
3. inpatient hospitalization or prolongation of existing hospitalization
4. a persistent or significant disability/incapacity
5. a congenital anomaly/birth defect

Other important medical events may also be considered an SAE when, based on appropriate medical judgment, they jeopardize the subject or require intervention to prevent one of the outcomes listed.

11.2.1 Serious Adverse Experience Reporting

All SAEs that occur (whether or not related to study drug) will be documented per UCSF CHR (IRB) Guidelines

(http://www.research.ucsf.edu/chr/guide/Violation_Incident_Guidelines.asp). The collection period for all SAEs will begin after informed consent is obtained and end after procedures for the final study visit (visit 2) have been completed.

In accordance with the standard operating procedures and policies of the local Institutional Review Board (IRB)/Independent Ethics Committee (IEC), the site investigator will report SAEs to the IRB/IEC.

11.3 Medical Monitoring

[name], is the Medical Monitor for this study and should be contacted directly at these numbers to report medical concerns or questions regarding safety.

[contact] [name]
[contact]

[name] will be the primary person responsible for study adverse event monitoring and will report adverse events and unanticipated problems to the UCSF IRB. All subjects will be monitored for possible adverse events and unanticipated problems throughout the study period.

12 DISCONTINUATION AND REPLACEMENT OF SUBJECTS

A subject may be discontinued from study treatment at any time if the subject, the investigator, or the Sponsor feels that it is not in the subject's best interest to continue. The following is a list of possible reasons for study treatment discontinuation:

- Subject withdrawal of consent (or assent)
- Subject is not compliant with study procedures
- Adverse event that in the opinion of the investigator would be in the best interest of the subject to discontinue his or her participation
- Protocol violation requiring discontinuation of study protocol
- Lost to follow-up
- Sponsor request for early termination of study
- Positive pregnancy test at visit 1 or self-reported pregnancy at visits 2 or 3

All subjects are free to withdraw from participation at any time, for any reason, specified or unspecified, and without prejudice.

Reasonable attempts will be made by the investigator to provide a reason for subject withdrawals. The reason for the subject's withdrawal from the study will be specified in the Subject Tracking Log ([Appendix F](#)) and the subject's CRF.

12.1 Withdrawal of Subjects from the Study

A subject may be withdrawn from the study at any time if the subject, the investigator, or the Sponsor feels that it is not in the subject's best interest to continue. This will be documented in the Subject Tracking Log ([Appendix F](#)) and the subject's CRF.

12.2 Replacement of Subjects

Subjects who withdraw from the study will be replaced.

13 PROTOCOL VIOLATIONS

A protocol violation occurs when the subject, research assistant(s), investigator, or Sponsor fails to adhere to significant protocol requirements affecting the inclusion, exclusion, subject safety and primary endpoint criteria. Protocol violations for this study include, but are not limited to, the following:

- Failure to meet inclusion/exclusion criteria
- Use of a prohibited concomitant medication or drug

Failure to comply with Good Clinical Practice (GCP) guidelines will also result in a protocol violation. The Sponsor will determine if a protocol violation will result in withdrawal of a subject.

When a protocol violation occurs, it will be discussed with the investigator and a Protocol Violation Form detailing the violation will be completed on the online UCSF CHR (IRB) portal (this form is reproduced in [Appendix J](#)). As requested by the UCSF CHR (IRB), the Sponsor and Principal Investigator will consult with the UCSF Privacy Office (<http://hipaa.ucsf.edu/>) when completing this form. This form will be electronically signed by the Principal Investigator. A printed copy of the form will be filed in the site's regulatory binder and in the Sponsor's files.

14 DATA SAFETY MONITORING

N/A

15 STATISTICAL METHODS AND CONSIDERATIONS

15.1 Data Sets Analyzed

All eligible subjects who are randomized into the study and complete, at a minimum, visit 2, will be included in analyses. [name], a statistician at the UCSF Osher Center for Integrative Medicine, will perform the data analysis for this study.

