4 STUDY DESIGN

4.1 Study Overview

This is a single center, double-blind, placebo-controlled, randomized, crossover trial that will include 24 subjects. Subjects will be in the study for up to 3 weeks. Total time involved will be approximately 5-6 hours. There will be a period of at least 24 hours between study Visits 1 and 2.

4.2 Total Study Duration:

Total duration of subject participation will be up to 3 weeks, with one session of web-based screening, one session involving a telephone screening call to confirm eligibility and introduce the subject to the study and two lab sessions involving administration of test and control products (first lab session includes urine screen). Total duration of the study, including recruitment and subject study completion, is expected to be 6 months.

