8.4.1 Dosage/Dosage Regimen

All subjects receive the control product and test product at different study visits (visits 1 and 2, which occur on different days). There will be a period of at least 24 hours between visits 1 and 2, as the period of time between each administration day does not impact analyses assessing primary or secondary outcomes. Subjects will be administered the test product (intranasal naloxone), 1 mg/1 mL per nostril, on one of their two visit days. Subjects will be administered the control product (intranasal placebo), 1 mL per nostril, on one of their two visit days.

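### The analysis set in Section 15.1 keeps only women who finish both dosing visits, so visit-1 data from women who do not return are dropped and any nausea-related non-return stays hidden

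*Combined protocol and SAP*

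**What the plan says.** Section 15.1 sets one rule for all analyses: "All eligible subjects who are randomized into the study and complete, at a minimum, visit 2, will be included in analyses". Section 15 defines no all-randomised, all-dosed or safety set beside it.

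Section 8.4.1 fixes the design: "All subjects receive the control product and test product at different study visits", namely visits 1 and 2. The schedule in Appendix E has only these two visits, and Section 11.2.1 calls visit 2 the final one. Section 12.2 adds: "Subjects who withdraw from the study will be replaced". It does not say whether the replacement takes the same sequence, or what happens to the data of the woman replaced.

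Outcomes are collected at visit 1 as well as visit 2. On nausea, Section 10 says: "Subjects will self-report their level of nausea (present versus absent) in the context of completing" the withdrawal scale, before dosing and at 10 and 30 minutes. Section 9.2.3 collects saliva for cortisol at both visits.

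The primary analysis (Section 15.3) is McNemar's test. Section 15.4 names a linear mixed model for cortisol.

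Some details do not match a two-visit schedule. Section 12 lists as a reason for discontinuation: "Positive pregnancy test at visit 1 or self-reported pregnancy at visits 2 or 3". Section 4.1 says: "Total time involved will be approximately 5-6 hours". Section 9 pays up to $50 "for completion of each study visit, and up to an additional" $50 at the end, with a stated maximum of $200.

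**The concern.** Under the current schedule, completing visit 2 means completing the trial. A woman who is dosed at visit 1, reports her symptoms, gives saliva and does not return contributes to no analysis. Her replacement brings the count back to 24, so the final data set shows no sign of her.

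Two things are at stake. First, the cortisol mixed model can use a woman with one visit, and the rule discards her for no statistical reason. Second, nausea is both the primary outcome and a plausible reason not to come back. If naloxone nausea at visit 1 deters return, the completers under-represent women who respond, and the observed nausea rate describes women who came back rather than all women dosed. Without a report on non-returners, a reader cannot tell whether this happened. Non-return unrelated to nausea causes no such bias.

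**Working it through.** **Which set the rule defines.** Dosing is at visits 1 and 2 (Section 8.4.1, Appendix E) and visit 2 is final (Section 11.2.1). Completing at least visit 2 therefore means completing both.

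**The plan's own figures.** The table row that sets N = 24 (30% v 60%, power .805) reproduces by the plan's stated method, with a Beta(r, N − r) weight and an assumed one-sided alpha of .05: .8046. The sample size is not in dispute here. The visit-related totals compare as follows:

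| Item | Two visits | Three visits | Stated |
|---|---|---|---|
| Payment | 2 × 50 + 50 = $150 | 3 × 50 + 50 = $200 | up to $200 |
| Hours, with two 15-minute screens | 3.5 to 4.5 | 5.0 to 6.5 | 5 to 6 |

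**Which analyses the rule affects.** McNemar uses only women with both responses, so a non-returner cannot enter it under any wording. The mixed model can use her three cortisol values.

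**Illustration of selection.** All inputs are assumptions, because the documents give no return rate:
- true nausea is q = .30 on naloxone and 0 on placebo;
- there are 12 completers per sequence after replacement within sequence;
- a fraction d of women nauseated on naloxone at visit 1 does not return.

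Only the naloxone-first sequence is affected. Its completer rate is r = q(1 − d)/(1 − qd). The overall completer rate is (r + q)/2. Expected women lost are 12qd/(1 − qd).

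| d | r | Completer rate | Women lost |
|---|---|---|---|
| 10% | .27/.97 = .278 | 28.9% | .36/.97 = 0.4 |
| 25% | .225/.925 = .243 | 27.2% | .9/.925 = 1.0 |
| 50% | .15/.85 = .176 | 23.8% | 1.8/.85 = 2.1 |

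In this illustration, exact two-sided McNemar power at alpha .05 (not stated in the plan) needs at least 6 discordant pairs, since 2 × .5⁶ = .031. It is .771 with full return and .735, .670 and .525 at the three values of d. These losses come from the assumed non-return, and changing Section 15.1 would not recover them.

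**What a two-direction fill would show.** Suppose every dosed woman is counted and missing responses are filled first in favour of a naloxone effect and then against it. The expected bounds on the difference are about 28.5 to 30, 26 to 30 and 22 to 30 points, against a true 30. The bounds widen with the number lost, which makes the uncertainty visible.

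**The case against.** The strongest reply is that the primary test is untouched: McNemar needs pairs, so the rule costs it nothing. That stands in full. Loss may also be small. Section 9 pays a completion bonus, and Section 10 books both visits at the phone screen, as little as 24 hours apart. At d = 10% the illustrated effect is 1.1 points and 0.4 of a woman. Withdrawal reasons and adverse events are already recorded. None of this answers the unnecessary loss to the cortisol model or the lack of any report on non-returners.

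A reader might infer that Section 15.1 survives from a three-visit plan in which visit 1 was a separate baseline, so that the rule once meant at least one dosing visit and the text leaves the meaning open. The documents do not support that. Section 11.2.1 settles that visit 2 is the last. The phone-screen entry "Schedule baseline assessment" fits the synopsis, which places the baseline assessment inside visit 1. The $200 is described as covering time and travel, so the $50 above the itemised sum need not be a third visit. Only the mention of a visit 3 in Section 12 names something that does not exist. The hours are a mismatch in logistics and do not alter the analysis set.

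A reader might also infer a risk of false positives. That needs placebo nausea alone to deter return, although women are blinded and the plan expects no placebo nausea. With 30% nausea on both products, one-sided error is .024 with full return and .028, .037 and .062 at d = 10%, 25% and 50%. It passes .05 only in the last case. With 10% on both it never exceeds .017. If nausea on either product deters equally, the expected difference stays at zero and the error falls slightly.

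**Conclusion.** The point holds as a minor, cheap improvement. Section 15.1 defines a both-visits completer set for every analysis and, with replacement, removes recorded visit-1 data from women who do not return. The avoidable costs are single-visit data in the cortisol model and the invisibility of any nausea-related non-return.

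The size of any bias is unknown. Under the assumptions above, the completer nausea rate falls by about 1, 3 or 6 points from 30% when 10%, 25% or 50% of women nauseated on naloxone at visit 1 stay away. The more plausible direction is against naloxone, and the opposite direction is an extreme case under blinding. It would be wrong to conclude that the primary test is invalid, that rewording would restore its power, or that the text is undecided about which visit is meant.

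**What to change.** 1. In Section 15.1, define the analysis set as all randomised women who received at least one product. State that replacements are added to those who withdrew and do not take their place in the data.
2. Fit the cortisol mixed model to every available visit.
3. Keep McNemar on complete pairs as primary, and state that it applies to women with both visits.
4. For all dosed women, tabulate visit-1 nausea by product received and by return. If anyone fails to return, add a sensitivity analysis filled in both directions: missing naloxone as nausea with missing placebo as none, then the reverse.
5. Reconcile the visit 3 reference in Section 12 and the total hours in Section 4.1 with the two-visit schedule, and check the payment total in Section 9.

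The cost is a few lines of wording, one table and a short sensitivity analysis. Visit-1 nausea, product given and withdrawal reason are already collected. The primary test gains nothing, and the bounds will be wide if several women withdraw.
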